#### **4.7 Subgroup analysis**

Protocol pre-specified subgroup analyses will be conducted using mixed-effects linear models or the GEE approach, consistent with the analyses proposed for each outcome as described previously. Pre-specified subgroups of interest are those defined by gender (women, men), race (Black, non-Black), baseline level of the outcome of interest, baseline number of medications used to treat the outcome, and chronic kidney disease status. The mean models for the analysis will be augmented with binary subgroup indicator(s) and appropriate cross-product interaction terms of subgroup indicator(s) by diet indicators. The differential intervention effects between subgroups will be evaluated through estimating the regression beta coefficient of the interaction terms and the corresponding 95% CIs. Subgroups with less than 10 participants will not be reported. The trial is not powered based on any specific subgroup analyses so these analyses are exploratory and will not be adjusted for multiple comparisons.

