## 6 STUDY POPULATION AND ELIGIBILITY

### 6.1 Study Population

The study population will consist of approximately 100 adults, ages 18 and older, who have Type 2 diabetes, a systolic BP of 120-159 mmHg, and diastolic BP <100 mmHg. We will attempt to enroll approximately one-third of participants from each of 120-129, 130-139, and 140-159 mmHg systolic BP ranges, about 50% women, and about 50% African-Americans.

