  - g. Diet acceptability, as rated by participants on two questions with a 9-point Likert scale for how much the participant liked the diet (1=disliked extremely, 9=liked extremely) and how hungry the participant felt while eating the diet (1=not at all hungry, 9=extremely hungry)

Additionally, safety outcomes including hypoglycemia, hypokalemia, hyperkalemia, elevated BP, low BP, serious adverse events [SAEs], and adverse medical events, which are assessed throughout each of the intervention periods, will also be documented for and compared across the study diets.

- 1.2.8 To conduct subgroup analyses (by gender, race, age, baseline level of the outcome variable [i.e., BP for the primary and secondary outcomes], baseline number of medications used to treat the outcome, and chronic kidney disease [CKD] status), corresponding to the above aims.
- 1.2.9 To establish a repository of biospecimens (plasma, serum, urine, stool, PAXgene).

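### SAP 4.7 tests effect modification by baseline blood pressure only through binary indicators; adding a numeric interaction would recover information at almost no cost

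*Combined protocol and SAP*

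**What the plan says.** SAP 4.7 gives two named levels each for gender and race. It then lists, without levels or cut points, "baseline level of the outcome of interest, baseline number of medications used to treat the outcome, and chronic kidney disease status". The coding rule for all of them is a single sentence: "The mean models for the analysis will be augmented with binary subgroup indicator(s) and appropriate cross-product interaction terms of subgroup indicator(s) by diet indicators". Results are judged as follows: "The differential intervention effects between subgroups will be evaluated through estimating the regression beta coefficient of the interaction terms and the corresponding 95% CIs". The section also limits its own claims: "The trial is not powered based on any specific subgroup analyses so these analyses are exploratory and will not be adjusted for multiple comparisons".

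Three other places bear on this:

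- SAP 1.2.8 includes age among the modifiers ("To conduct subgroup analyses (by gender, race, age, baseline level of the outcome variable"), as does objective 9 in protocol section 4.5. SAP 4.7 does not mention age.
- Protocol section 6.1 sets a recruitment target for the main modifier: "We will attempt to enroll approximately one-third of participants from each of 120-129, 130-139, and 140-159 mmHg systolic BP ranges".
- Protocol section 8.1 (Table 4) bases final BP eligibility on the mean of nine readings from three screening visits, so a well-measured numeric baseline exists.

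**The concern.** Whether the diets lower BP more in people who start higher is a pre-specified question, and recruitment deliberately spreads baseline systolic BP over 120-159 mmHg. Replacing that measurement with an indicator treats everyone on one side of a cut as alike and separates people just either side of it. If the diet effect changes gradually with baseline BP, the indicator carries only part of the available information. The interaction CI becomes wider than it need be, and the estimate depends on a cut the plan does not name. With 100 participants and no power claim for subgroups, there is little precision to spare.

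**Working it through.** **Inputs from the documents (SAP section 3; protocol 6.1).** N = 100; cross-sectional SD 14 mmHg; within-person correlation 0.75; SD of the between-period difference 9.9 mmHg; two-sided 5% level; recruitment thirds in 120-129, 130-139 and 140-159 mmHg.

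**Assumed, not in the documents.** Thirds achieved, uniform spread within bands (120-130, 130-140, 140-160); linear modification of the DL-CH effect with slope b (mmHg per mmHg of baseline); 9.9 mmHg as the residual SD of each participant's DL-CH difference; the cut points.

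**1. The plan's own figures.** SD of difference = 14 × √(2 × (1 − 0.75)) = 9.90, which matches. Minimal detectable difference at 90% power = (1.960 + 1.282) × 9.90 / √100 = 3.21 mmHg, or 3.24 with the noncentral t, against 3.34 stated. The stated value is slightly conservative. The SAP gives no figure for subgroup interactions.

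**2. Variance of baseline SBP.** Band means are 125, 135 and 150; the overall mean is 136.67.

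- Within bands: (100/12 + 100/12 + 400/12) / 3 = 16.67
- Between bands: (11.67² + 1.67² + 13.33²) / 3 = 105.56
- Total: 122.22, so SD = 11.06 mmHg

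**3. Information kept by one split.** R = p(1 − p) × (difference in group means)² / total variance.

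- Cut at 130: (1/3)(2/3)(142.5 − 125)² / 122.22 = 0.557, so 44% lost
- Cut at 135 (median): (1/2)(1/2)(145.83 − 127.5)² / 122.22 = 0.688, so 31% lost
- Cut at 140: (2/3)(1/3)(150 − 130)² / 122.22 = 0.727, so 27% lost
- Three bands as two indicators: 105.56 / 122.22 = 0.864, so 14% lost

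Other distributions were tried: uniform on 120-160, five truncated normals, and a plain normal for median splits. A cut at 130 then loses 42-55%, a cut at 140 loses 25-40%, a median split 25-36%, and the three bands 14-20%.

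**4. Power.** Noncentrality = b × 11.06 × √100 / 9.9, multiplied by √R for a split; t with 98 df. For the three bands, a joint F test with 2 and 97 df.

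| Slope b | Numeric | Cut 130 | Cut 135 | Cut 140 | Three bands (joint) |
|---|---|---|---|---|---|
| 0.10 | 20% | 13% | 15% | 16% | 14% |
| 0.15 | 38% | 24% | 28% | 29% | 26% |
| 0.25 | 79% | 54% | 63% | 65% | 62% |

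On scale: across 40 mmHg of baseline, a slope of 0.15 means the effect varies by 0.15 × 40 = 6 mmHg. A slope of 0.25 means 10 mmHg, which exceeds the entire 8.9 mmHg DASH-Sodium effect quoted in SAP section 3.

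**5. When the binary term wins.** Suppose the effect jumps by 6 mmHg exactly at 140. Noncentrality for the 140 split is 6 × √(2/9) × 10 / 9.9 = 2.86, giving about 81% power (82% by simulation). The numeric term has 2.86 × √0.727 = 2.44, giving 67%.

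**The case against.** The best defence is that the plan does not commit to two groups. The plural form for indicators is ordinary wording for the dummy variables of a multi-level factor. The only SBP grouping in the documents has three bands, and the CGM appendix (section 11.3) uses three levels for medication count and for HbA1c. A reader might therefore infer that SAP 4.7 dichotomises baseline BP and throws away 27-44% of the information; the text fixes neither a cut nor the number of groups, so that range is not a property of the plan. This part of the defence stands. It reduces the problem without removing it: with three bands the information loss is small, but the joint test spends an extra degree of freedom and ends with about the power of a median split.

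A reader might also extend the point to every numeric modifier. The documents do not support that. SAP 4.7 gives no coding for age because it omits age, and no loss can be computed for medication count, whose distribution is not given and for which a constant effect per drug would itself be a strong assumption.

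Nor does it follow that the trial would wrongly conclude that baseline BP is irrelevant. SAP 4.7 calls these analyses exploratory and unpowered and reports estimates with CIs, and nothing in the SAP proposes reading a wide interval as absence of effect.

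Finally, the shape of any modification is unknown, a step would favour the indicator, and at modest slopes both codings have low power. All of that is right. It limits the gain but is not a reason to leave the numeric term out.

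**Conclusion.** The point holds in a limited form. SAP 4.7 evaluates modification by baseline outcome level and medication count through binary indicators alone, with no numeric interaction and no stated cuts. For baseline SBP under roughly linear modification, the loss is about 25-55% of the information for a single split, depending on the cut and distribution (27-44% for cuts at 140 and 130 under the recruitment target), and 14-20% for three bands. In power terms that is 9 to 14 points at a slope of 0.15 and 14 to 25 points at the large slope of 0.25 for a single split. These sizes rest on linearity, the assumed baseline distribution and the SAP's 9.9 mmHg. They apply to baseline SBP only. The primary contrast and the other main estimates are unaffected. It is a cheap improvement to an exploratory section, to be considered rather than required.

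**What to change.** Amend SAP 4.7 as follows:

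- For continuous outcomes, and at least for SBP and DBP, base the interaction inference for baseline level on the centred numeric baseline crossed with the diet indicators. For BP, use the nine-reading screening mean. Report the change in diet effect per 10 mmHg with its 95% CI.
- Add age to SAP 4.7, so that it agrees with SAP 1.2.8, and treat it the same way, per 10 years.
- For outcomes analysed by GEE, put the numeric modifier in the corresponding GEE mean model where a numeric baseline exists. A yes/no outcome such as orthostatic hypotension has no such baseline and stays categorical.
- Keep categories for display and state them in advance, for example the 120-129, 130-139 and 140-159 mmHg bands, so that readers can check linearity. Medication count may stay in stated categories. Gender, race and CKD status stay as planned.

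The cost is a few sentences and one changed model term, with no new data or visits. The downside is the assumption of an approximately linear trend, which the displayed categories help to check.

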### 3 POWER AND SAMPLE SIZE

The trial aims to enroll 100 eligible participants. This sample size goal is selected based on resources and logistic considerations, after confirmation of sufficient statistical power to detect meaningful minimal detectable difference (MDD) for the primary testing contrast (see 1.1) under plausible and yet conservative parameter scenarios, as detailed below.

Minimal Detectable Difference (MDD) for systolic blood pressure (SBP) reduction between DASH4D diet with lower sodium (DL) and the comparison diet with higher sodium (CH), with 2-sided type 1 error of 0.05 and 90% power. The observed effect from the DASH-Sodium trial was 8.9 mmHg.			
Sample Size (N)	Standard Deviation (SD)	Within-person Correlation (r)	Minimal Detectable Difference (MDD), mmHg
100	14	0.5	4.71
100	14	0.75	3.34
90	14	0.5	4.99
90	14	0.75	3.53
80	14	0.5	5.28
80	14	0.75	3.84
100	12	0.5	4.04
100	12	0.75	2.86
90	12	0.5	4.28
90	12	0.75	3.03
80	12	0.5	4.53
80	12	0.75	3.21

Data from DASH-Sodium trial showed that cross-sectional SD for SBP at baseline and after intervention ranged from 9.4 to 11.9 mmHg across intervention arms. We conservatively assumed a cross-sectional SD of 14 mmHg and within-person correlation between SBP measures from different end-of-feeding periods of 0.75, which would result in a SD for SBP difference between feeding periods of 9.9 mmHg, a value that is conservative compared to previous trials with similar designs for different patient populations (e.g., 6.1 mmHg from OmniHeart, and between 7.4 and 9.2 mmHg across arms of DASH-Sodium).

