4 STATISTICAL ANALYSIS FRAMEWORK

4.1 Overview

This trial is a randomized, four-period crossover study that tests the effects of 4 diets (specified by the combinations of 2 diet factors – DASH4D vs Comparison and 2 sodium levels – Higher vs Lower) on a specified set of outcomes. The 4 diets are denoted DH (DASH4D-Higher sodium), CH (Comparison-Higher sodium), DL (DASH4D-Lower sodium), and CL (Comparison-Lower sodium). Each participant receives all 4 diets. Each diet is eaten for 5 consecutive weeks. The order in which participants eat these diets is random. A break of at least 1 week (typically 2 weeks), where participants are eating their own food, will separate each consecutive set of feeding periods.

		DIETARY PATTERN	
		Comparison	DASH4D
SODIUM LEVEL	Higher (3700mg)	CH (ref*)	DH
	Lower (1500 mg)	CL	DL

\*reference group for the primary contrast

The primary outcome of the trial is end-of-period systolic BP (SBP), with the primary contrast testing the mean SBP difference between the DL and the CH diets (Primary Aim). The secondary contrasts focus on the effects of sodium on SBP stratified by diet types (DH vs DL and CH vs CL, Secondary Aim 1.2.1), and the effect of diet on SBP stratified by sodium levels (DH vs CH and DL vs CL, Secondary Aim 1.2.2). The trial will examine whether the diet and sodium effects are additive through exploring for diet-sodium interaction on SBP (Secondary Aim 1.2.3), and assess the time course of the sodium effects on SBP by diet types (Secondary Aim 1.2.4) and the diet effects on the time course of SBP by sodium levels (Secondary Aim 1.2.5) over the 5-week feeding period. We will also assess the effects of these diet contrasts on other protocol-specified outcomes, namely, diastolic BP (DBP; Secondary Aim 1.2.6), fasting glucose, fructosamine, plasma lipids, CVD risk scores, patient-reported outcomes, and specified safety outcomes, SAEs and adverse medical events (Secondary Aim 1.2.7). We will assess the differences of the aforementioned outcomes under the specified diet contrasts by pre-specified subgroups (Secondary Aim 1.2.8).

Aim	Outcome	Timing	Contrast
Primary 1.1	SBP	End of Period	CH vs DL
Secondary 1.2.1	SBP	End of Period	DH vs DL; CH vs CL
Secondary 1.2.2	SBP	End of Period	DH vs CH; DL vs CL
Secondary 1.2.3	SBP	End of Period	(DH-DL) vs (CH-CL)*
Secondary 1.2.4	SBP	Period Trajectory	DH vs DL; CH vs CL
Secondary 1.2.5	SBP	Period Trajectory	DH vs CH; DL vs CL

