Secondary 1.2.6	DBP	Same as all of above for SBP	
Secondary 1.2.7	fasting glucose; glycated albumin; fructosamine; HbA1c; plasma lipids; 24-hour urinary albumin excretion; CVD risk score; patient-reported outcomes	End of Period	CH vs DL; DH vs DL; CH vs CL; DH vs CH; DL vs CL; (DH-DL) vs (CH-CL)*
	safety data (incl. hypoglycemia, hyperkalemia, elevated BP, low BP, SAEs & adverse medical events)	Cumulative over the entire period	CH vs DL; DH vs DL; CH vs CL; DH vs CH; DL vs CL; (DH-DL) vs (CH-CL)*
Secondary 1.2.8	All of above, by pre-specified subgroups		

\*examination of interaction (difference of differences)

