The safety outcomes of count data (or binary variables) will be analyzed using generalized estimating equations (GEE) approach, to derive population-average inferences while accounting for the correlation of outcome data from different feeding periods within the same participant. The mean model will be constructed similarly to the mean models used in the mixed-effects regression analysis previously described (e.g., same parametrization of predictors). Log link will be used for count outcomes and logit link will be used for binary outcomes. Unstructured working correlation will be used, and robust standard errors will be derived for statistical inferences. The potential for overdispersion in the count data will be explored, and negative binomial models will be used when appropriate.

Similar analytic strategies will be used for exploration of additional relevant outcomes that are not specified in the Aims.

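### Count outcomes in subgroups of 10 to 20: the SAP's GEE robust standard errors name no small-sample correction, so nominal 95% intervals for subgroup-by-diet interactions come out too narrow

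*Combined protocol and SAP*

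**What the plan says.** The aims table in SAP 4.1 gives the scope of Aim 1.2.8 as "All of above, by pre-specified subgroups". The rows above it include the safety data, so count outcomes fall within the subgroup plan.

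SAP 4.7 fits each subgroup analysis with the method already chosen for the outcome, mixed model or GEE: "The mean models for the analysis will be augmented with binary subgroup indicator(s) and appropriate cross-product interaction terms of subgroup indicator(s) by diet indicators". Differential effects are judged from the interaction coefficients and their 95% intervals. The reporting floor is "Subgroups with less than 10 participants will not be reported". The section calls these analyses exploratory, not powered and not adjusted for multiplicity.

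For GEE outcomes, SAP 4.6 says "Log link will be used for count outcomes and logit link will be used for binary outcomes". On variance it says "Unstructured working correlation will be used, and robust standard errors will be derived for statistical inferences". On overdispersion it says "The potential for overdispersion in the count data will be explored, and negative binomial models will be used when appropriate". Neither section mentions a small-sample variance correction, a t reference or a minimum number of events.

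**The concern.** A robust (sandwich) variance is built from observed residuals, one cluster per participant. Its validity depends on the number of clusters. The trial has about 100, but a contrast within a subgroup of 10 draws its variance essentially from those 10 people. In the interaction, which subtracts the complement's contrast, the small group dominates. Fitted residuals are smaller than true errors, so the variance is biased downward. The normal reference also ignores how poorly that variance is estimated.

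The floor of 10 is in effect the SAP's statement that an interval from 10 participants is fit to report. If such an interval covers less than its label says, a small subgroup will too often appear to tolerate a diet better or worse than the rest. CKD status is where this could matter most. Protocol 7.1 expects some participants with early CKD, protocol 10.3 treats eGFR below 60 as a risk factor for hyperkalemia, and Table 2 sets potassium at 3900 against 1950 mg/day.

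**Working it through.** The plan states no coverage figure or event rate for these analyses, so there is no figure of its own to reproduce.

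**Inputs from the documents.** "The trial aims to enroll 100 eligible participants" (SAP 3). "Each participant receives all 4 diets", so each cluster has four period records (SAP 4.1). The links, unstructured working correlation and robust errors are from SAP 4.6. The interaction model and the floor of 10 are from SAP 4.7.

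**Assumed inputs.** Event rates of 0.1, 0.3, 0.5, 1 and 2 per person-period. Overdispersion is none; moderate (person-level gamma variance 0.5, period-level 0 or 0.5); or strong (person-level variance 1).

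**Step 1, a hand check of the mechanism.** Take the simplest case: a mean paired difference between two diets in m people, with normal errors. The plain sandwich variance is Σr²/m² = [(m−1)/m]·s²/m. Its nominal 95% interval therefore covers P(|t(m−1)| < 1.96·√[(m−1)/m]).

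- m=10: 1.96 × √0.9 = 1.859; coverage 90.4%.
- m=15: 1.96 × √(14/15) = 1.894; coverage 92.1%.
- m=20: 1.96 × √0.95 = 1.910; coverage 92.9%.

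Skewed, overdispersed counts should do worse than this normal case.

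**Step 2, simulation of the SAP's model.** N=100, four periods, random diet orders, log-link GEE with period, diet, subgroup and subgroup-by-diet terms, unstructured working correlation, interval = estimate ± 1.96 robust SE. There were 3000 replicates per scenario; the Monte Carlo error is about √(0.9×0.1/3000) = 0.5 point. Coverage of the interaction interval:

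| Scenario | n=10 | n=15 | n=20 |
|---|---|---|---|
| Rates 0.5-2, no overdispersion | 90.6-92.8% | 92.0-92.1% | 92.9-93.4% |
| Rates 0.5-2, moderate | 86.3-91.3% | 89.3-92.5% | 90.5-91.8% |
| Rates 0.5-2, strong | 83.3-88.9% | 86.8-90.9% | 88.7-91.4% |
| All with rate 0.3 or more | 83.3-93.4% | 86.8-94.4% | 88.7-94.0% |

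A separate simulation at 0.5-1 events and moderate overdispersion gave 89-92% at n=10 and 91-93% at n=20. Together the two give the rounded moderate-overdispersion ranges of 86-92% and 90-93%.

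**Step 3, variants.**

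- A negative-binomial variance (moderate or strong overdispersion, n=10-20) does not remove the shortfall: 85.1-91.4%.
- The within-subgroup diet effect is somewhat worse than the interaction: 80.3-93.5% at n=10 for rates of 0.3 or more.
- Binary outcomes at risk 0.3-0.5: 91.7-94.0%.
- Subgroups of 50 at rates of 0.3 or more: 91.2-94.8%.

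**Step 4, the correction.** Mancl-DeRouen replaces each participant's residual vector r by (I−H)⁻¹r, where H is that participant's leverage block. The reference is t with n−1 degrees of freedom, n being the smaller subgroup. At rates 0.5-2 with moderate overdispersion, interaction coverage becomes 94.4-96.3% (n=10), 93.8-96.4% (n=15) and 94.2-95.1% (n=20). With strong overdispersion it is 92.0-95.5% over the three sizes. With no overdispersion it is slightly conservative at n=10 (96.3-98.0%).

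**Step 5, sparse events.** At 0.1 events per person-period, 36-41% of fits converge at n=10 and 67-73% at n=20. Among those that converge, corrected coverage is still only 74-90% over n=10-20.

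**The case against.** Several points on the other side are sound.

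- **The SAP does not say the variance is uncorrected.** It says only that it is robust. An analyst could apply a correction and still comply. That stands; the point is that nothing in the plan requires one, and the unqualified term is ordinarily read as the plain sandwich.
- **The size is assumed.** A reader might infer that these intervals cover a fixed 86-91%. The documents do not support a single figure, because they give neither rates nor overdispersion.
- **Binary outcomes and larger groups.** A reader might extend the point to every GEE outcome and every subgroup. Binary outcomes at moderate risk lose only one to three points. Protocol 6.1 plans about 50% women, about 50% African-Americans and about a third in each systolic BP band, so those groups are well above 20.
- **The interaction does not rest on the small subgroup alone.** Its complement also contributes, which is why its coverage is somewhat better than that of the within-subgroup contrast.
- **Safeguards exist.** SAP 4.7 labels the analyses exploratory. SAP 4.1.4 asks for biological coherence, warnings about chance and independent confirmation of unexpected findings. These temper interpretation, but they do not make a 95% label accurate.
- **Missing data.** SAP 4.1.2 plans multiple imputation before GEE. The simulations had complete data, so that step was not examined.

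**Conclusion.** The point holds as a conditional one. If the plain sandwich variance with a normal reference is used, interaction intervals for count outcomes in subgroups of 10 to 20 fall short of 95%. Under moderate overdispersion at n=10, the main simulation's chance of a false signal is 8.7-13.7% (100 minus 91.3 and 86.3), or 1.7 to 2.7 times the nominal 5%. Without overdispersion it is 7.2-9.4%, or 1.4 to 1.9 times.

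The exposed groups are probably CKD status and medication-count categories. That is itself an assumption, since neither size is stated and SAP 4.7 gives no cut points for medication count. For very rare events, failed fits and empty cells are a larger problem than the variance estimator, and a floor counted in participants does not address them.

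Nothing here supports a stronger reading in which the primary systolic BP contrast or the other BP analyses are compromised. Those use mixed models that estimate a covariance from the whole sample.

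**What to change.** Add to SAP 4.7:

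- For outcomes analysed by GEE, subgroup-specific contrasts and subgroup-by-diet interactions will use a bias-corrected sandwich variance (for example Mancl-DeRouen), with a t reference on the number of participants in the smaller subgroup minus 1.
- A minimum event count per subgroup, below which only descriptive counts are reported. The team should choose the number before seeing subgroup results by diet.

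The floor of 10 participants and the mixed-model subgroup analyses can stay.

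The cost is two SAP sentences, a software option and wider intervals. At n=10 the critical value rises from 1.96 to 2.26, about 15%. With the variance correction, the paired illustration widens by a factor of (2.262 × √(10/9)) / 1.859 = 1.28. At n=20 the same factor is (2.093 × √(20/19)) / 1.910 = 1.12.
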